10.5 Sample Size

We will randomize 400 participants using a 3:1 allocation, resulting in 300 participants in the intervention group and 100 participants in the usual care group. While we will aim to minimize participant dropout, we include adjustment for up to 20% dropout in each arm, resulting in about 320 participants with evaluable endpoints (240 intervention, 80 usual care). We wish to be able to detect a clinically meaningful difference between groups in our primary efficacy endpoint, change in 6MWD from baseline to 3 months. A recent meta-analysis⁵⁷ found an average difference in 6MWD of about 60 meters before and after traditional CR. Perera et al. determined this degree of change in 6MWD to be clinically meaningful based on its relationship to other health status measures.⁹⁸ Minneboo et al., however, also estimated an improvement in 6MWD in a control group of approximately 35 meters.⁵⁹ We therefore require adequate power to detect a difference between groups of less than 25 meters in change in 6MWD (i.e., the difference between a 60-meter improvement in the intervention group and a 35-meter improvement in the usual care group); this is the same amount estimated by Gremeaux et al. as a minimal clinically important difference in patients with IHD.⁹⁹ Assuming a conservative standard deviation estimate of 60 meters,⁵⁷ 320 participants provide approximately 90% power to detect a difference between groups of 25 meters, using a two-sided, 0.05-level test; there is 80% power to detect a difference

CONFIDENTIAL

This material is the property of the NYU School of Medicine and Langone Medical Center. Do not disclose or use except as authorized in writing by the study sponsor

between groups as small as 22 meters. This sample size also provides at least 80% power to detect reasonable effect sizes in secondary endpoints.

While the sample size was determined to provide sufficient power to detect a clinically meaningful difference in the primary outcome of 6MWD, it enables comparisons of secondary efficacy endpoints as well. The table below shows clinically meaningful effect sizes for these outcomes, and gives the power to detect these effect sizes

CONFIDENTIAL

This material is the property of the NYU School of Medicine and Langone Medical Center. Do not disclose or use except as authorized in writing by the study sponsor

with our expected sample of 320 patients, using two-sided, 0.05-level tests; we will not implement multiple comparisons correction for these secondary outcomes. Baseline event rates and standard deviations are estimated from the literature.¹¹⁵⁻¹¹⁸ For example, we have 90% power to detect a difference between groups of 5 units in the SF-12 score.

All comparisons between the randomized groups in this trial will be performed according to the principle of "intention-to-treat"; that is, participants will be analyzed according to the treatment group to which they were randomized, regardless of subsequent crossover. The intent-to-treat (ITT) population will include all subjects who receive a randomized treatment assignment, except for those with a documented violation of trial eligibility criteria.

The table below shows clinically meaningful effect sizes for secondary efficacy outcomes, and gives the power to detect these effect sizes with our expected sample of 320 patients, using two-sided, 0.05-level tests; we will not implement multiple comparisons correction for these secondary outcomes.

Outcome	Endpoint definition	Effect size	Estimated s.d.	Power
Goal attainment scaling	GAS score	5	15	73%
Health status	SF-12	5	12	90%
Health status	Residual angina on SAQ	15-20%	n/a	67-93%
ADLs	Standardized ADL score	15-20%	1	64-87%
Hospital readmission	Admission by 3 months	15%	n/a	91%
Death	Death by 3 months	10%	n/a	82%

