- *3-month ambulatory assessment (all participants).* The research coordinator will schedule an ambulatory visit to take place 3 months after the baseline assessment. For NYU patients, this visit will occur at a designated research space in the main hospital campus (NYU Tisch Hospital). For participants at NYULH-Winthrop, the visit will be performed at the outpatient office of the FGP of Winthrop Cardiology Associates located at [name]. For UMMHC patients, this visit will take place at the Ambulatory Care Center (1st floor) at [name]. For participants at the Bellevue site, the CTSI Bellevue research suites or designated areas in the NYU main hospital campus will be used. For Yale patients, this visit will take place at ambulatory space adjacent to Yale-New Haven Hospital. The estimated time for the 3-month visit is 1 hour. Measures at 3 months will include a repeat of several baseline instruments to evaluate change over time (weight, BP, SF-12, SAQ-7, ADLs, PHQ-8). Participants will also be asked about hospital readmissions since time of last visit. 6MWT and Goal Attainment Scaling will be performed by the research nurse and/or a blinded assessor.

The Fitbit, portable tablet computer, and BP cuff will be collected. The research coordinator will also perform chart abstraction at 3-months to evaluate ambulatory CR attendance, and to verify self-report of hospital readmissions. For readmissions that occur outside the NYU, Bellevue, UMass or Yale systems, hospital records will be obtained.

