7.2.3 Intermediate Visits

7.2.3.1 Home activities (Day 2-89)

- (All participants): Record all participants' Activities of Daily Living Assessment data once every two weeks during the first month, and then monthly during months 2 and 3 (+ 5 days post due date).
- (Intervention Participants only): Record participants' adherence to mHealth-CR program from Moving Analytics and FitBit platform
 - Daily therapist-directed activity (walking, jogging, etc.)
 - Weekly video education
 - FitBit tracking and review of steps
 - Daily mHealth data entry
- Record participants' weekly blood pressure data.
- Administer weekly therapist phone calls for counseling/activity review (+ 5 days post due date).
- Record adverse events as reported by participant or observed by investigator.

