Health status at 3 months will be assessed using linear regression with adjustment for baseline levels and a binary treatment indicator; if necessary, health status scores will be log-transformed to improve the approximation to normality. Activities of daily living (BADLs and IADLs) will be assessed using longitudinal models for interval scores, with indicators to incorporate time, a binary indicator of treatment group, and patient-level random effects to accommodate repeated assessments within individuals; if interval scores are not approximately normally distributed, suitable transformations will be sought. Hospital readmission and death will be evaluated using Kaplan-Meier estimates and tested with logrank statistics, as well as investigated using Cox proportional hazard models with adjustment for confounders if necessary. As with the models for the primary outcome, in each model described we will assess the need for adjustment for confounders using the change-in-estimate criterion.

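### Section 10.5 states at least 80% power for the secondary endpoints, but its own table gives 73% for GAS and ranges for SAQ and ADLs that begin at 67% and 64%

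*Combined protocol and SAP*

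**What the plan says.** Section 10.5 sizes the trial on the change in 6MWD and then adds, for the secondary endpoints: "This sample size also provides at least 80% power to detect reasonable effect sizes in secondary endpoints". It goes straight on to a table: "The table below shows clinically meaningful effect sizes for these outcomes, and gives the power to detect these effect sizes". The lead-in is repeated just above the table, which "gives the power to detect these effect sizes with our expected sample of 320 patients, using two-sided, 0.05-level tests". The evaluable number is 80% of the 400 randomized, split 240 to intervention and 80 to usual care. No multiplicity correction is planned for these outcomes.

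The table prints:

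| Outcome | Effect | SD | Power |
|---|---|---|---|
| GAS score | 5 | 15 | 73% |
| SF-12 | 5 | 12 | 90% |
| Residual angina (SAQ) | 15-20% | n/a | 67-93% |
| ADLs, standardized score | 15-20% | 1 | 64-87% |
| Readmission by 3 months | 15% | n/a | 91% |
| Death by 3 months | 10% | n/a | 82% |

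Event rates and SDs are attributed to cited literature; the event rates themselves are not printed.

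**The concern.** The sentence and the table describe the same sample and the same tests, yet they disagree. A floor of 80% implies a false-negative risk of no more than 20% at the effects of interest. The table implies 27% for GAS (100 - 73), and 33% and 36% at the lower effects for SAQ and ADLs.

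This matters when results are read. If GAS shows no significant difference, a reader relying on the sentence would take that as stronger evidence against a 5-point benefit than the plan's own figure supports. GAS heads the list of secondary endpoints in Sections 3.2, 4.2.2 and 10.2, so it is a row that readers will look at.

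**Working it through.** **Inputs (all Section 10.5).** n = 240 and 80; two-sided alpha 0.05; effects and SDs as in the table.

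**Formula.** For a difference δ with standard deviation σ, power ≈ Φ[δ / (σ·√(1/240 + 1/80)) − 1.96]. The root is √0.016667 = 0.1291. The noncentral t version is given beside it.

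**Step 1: reproduce the plan's figures.**
- 6MWD, 25 m, SD 60: 0.4167/0.1291 = 3.227; 3.227 − 1.96 = 1.267; power 89.8% (t: 89.6%). Printed: about 90%.
- 6MWD, 22 m, SD 60: 0.3667/0.1291 = 2.840; 2.840 − 1.96 = 0.880; power 81.1% (t: 80.8%). Printed: 80%.
- SF-12, 5 points, SD 12: the ratio is again 0.4167; power 89.8% (t: 89.6%). Printed: 90%.
- GAS, 5 points, SD 15: 0.3333/0.1291 = 2.582; 2.582 − 1.96 = 0.622; power 73.3% (t: 73.0%). Printed: 73%.

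The GAS entry is therefore sound on its stated inputs. The sentence is what fails.

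**Step 2: GAS difference detectable with 80% power.** (1.96 + 0.842) × 0.1291 = 0.362 SD (t: 0.363). At SD 15 that is about 5.4 points, against the tabulated 5.

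**Step 3: compare each row with 80%.**
- At or above throughout: SF-12 (90%), readmission (91%), death (82%).
- Below at its only effect: GAS (73%).
- Below at the lower effect and above at the upper: SAQ (67%, 93%), ADLs (64%, 87%).

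**Step 4: which rows can be checked at all.**
- *Binary rows.* The control rates are not given. Under assumed rates, with a normal approximation and 240 versus 80, the printed figures look attainable: readmission 91% needs a control rate near 23%, and death 82% one near 14%. For SAQ, a 45% control rate gives 68.5% and 91.2%, close to print but not exact. Over control rates of 30% to 80%, power for a 15-point SAQ difference runs from 64% to 82%.
- *ADL row.* If the effect is 0.15-0.20 SD at a single time point, the formula gives 21% and 34%, not 64% and 87%. The printed power matches 0.30-0.40 SD (t: 63.9%, 87.1%). It can also be recovered with every printed cell left as it is, using inputs that the documents do not state. One example is the baseline-adjusted mean of four follow-ups with an assumed correlation of 0.75: the variance factor is (1 + 3 × 0.75)/4 − 0.75² = 0.25, so the effective SD is 0.5. Another is 15-20% of an assumed mean of 2 SD, which is 0.30-0.40 SD.

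**The case against.** **The sentence is loose summary wording, and the table discloses the true figures directly after it.** That is fair as to seriousness: nothing is hidden, GAS misses by less than half a point (5.4 against 5), and SAQ and ADLs pass 80% within their ranges. Only GAS contradicts the sentence outright. But *reasonable* does not rescue it. The tabulated effects are the only secondary effects given, and the text calls them clinically meaningful. If *reasonable* means something larger, the sentence says nothing, since any trial has 80% power for a large enough effect. With no dropout (300 versus 100) GAS would reach 82%, but that is not the stated basis.

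**The row reflects only one GAS analysis.** This stands. A difference of 5 cannot occur on a scale from -2 to +2, so the row must describe the T-score t-test. Section 10.4.3 lists a rank-sum test first, and no power is given for it.

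**A reader might infer that the trial is too small.** The documents do not support that. The sample size was set on 6MWD, whose power reproduces, and nothing commits the design to 80% for GAS beyond this one sentence.

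**A reader might infer that the ADL power is wrong and should be 21-34%.** The documents do not support that either. Section 10.4.3 plans a longitudinal model with "patient-level random effects to accommodate repeated assessments within individuals", and Section 7.2.3.1 schedules ADL calls "once every two weeks during the first month, and then monthly during months 2 and 3": four calls, with a further assessment at the 3-month visit. A single-time-point formula is not the planned analysis, so failing to match it does not show an error. No cell in that row can be called wrong.

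**Conclusion.** The 80% sentence is wrong as written. At the plan's own effects and sample, GAS has 73% power, and SAQ and ADLs fall below 80% at the lower end of their ranges; three of the six rows meet the statement throughout. The GAS result needs no assumption beyond the printed effect, SD, group sizes and alpha. The SAQ and ADL statements take the table's power at face value, because their inputs are incomplete.

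The correction is worth making, but its reach is limited: it concerns secondary endpoints only, and the 6MWD power and the sample size are untouched. The missing ADL and control-rate inputs are a point of completeness, not an arithmetic error, and no replacement power for ADLs follows from the documents.

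**What to change.** Replace the 80% sentence in Section 10.5 with a summary that matches the table, for example: *At the tabulated effects, power is at least 80% for SF-12, readmission and death. It is 73% for GAS, where 80% power requires a difference of about 5.4 points at SD 15. For residual angina and ADLs it is 80% or more only toward the upper part of the effect ranges shown.*

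As a side note for completeness, state what the ADL effect of 15-20% is a percentage of, how many assessments and what within-person correlation its power assumes, and how baseline enters the model. Add the control rates behind the SAQ, readmission and death rows. The existing ADL power should stay until its authors supply these inputs.

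The cost is a text edit and a slightly less favourable statement about the secondary endpoints. No participants are added, and no analysis changes.

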- *Hospital readmission* is defined as an overnight stay (including observation) in any hospital within 3 months of discharge. Readmissions in older adults with IHD are common, costly, and disruptive; multiple entities within the U.S. healthcare system emphasize reducing potentially preventable readmissions.⁷² Since these data are obtainable via the electronic health record (EHR), we will also ascertain readmission events at 6 months and 1 year.
- *Death* is defined by death from any cause within 3 months of enrollment. Given our sample size, we do not expect to detect a significant difference in mortality rates, but a descriptive analysis may place other endpoints in context. In addition, absolute mortality rates can assist with planning of subsequent studies. Similar to readmission, we will also ascertain death at 6 months and 1 year through the EHR.

Safety Endpoint. The safety endpoint will be assessed at the 3-month ambulatory visit and includes (1) fall-related injury (operationalized as any fall requiring acute medical care); (2) hospitalization for acute coronary syndrome; and (3) hospitalization for unstable arrhythmia. Separately, among intervention participants, study staff will monitor potential exercise-related adverse events on an ongoing basis. Points of contact will include weekly phone calls with the exercise therapist as well as electronic communication via the mHealth app which is checked daily. All adverse events will be reported directly to the Principal Investigator and to the DSMB. In order to reduce the likelihood of these events, participants will complete the baseline 6MWT in-hospital; if any adverse event occurs during 6MWT (drop in SBP ≥ 15 mmHg, chest pain, ventricular arrhythmia), participants will be removed (not randomized). Other exclusion criteria (severe osteoarthritis, recent joint replacement,

CONFIDENTIAL

This material is the property of the NYU School of Medicine and Langone Medical Center. Do not disclose or use except as authorized in writing by the study sponsor

moderate or severe cognitive impairment) are also intended to minimize risk. Prior studies of home-based CR have reported that adverse events are uncommon.^{73,74}

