5.2 Exclusion Criteria

An individual who meets any of the following criteria will be excluded from participation in this study:

1. Non-ambulatory.
2. Moderate or severe cognitive impairment.

CONFIDENTIAL

This material is the property of the NYU School of Medicine and Langone Medical Center. Do not disclose or use except as authorized in writing by the study sponsor

3. Unable/unwilling to consent.
4. PCI-related groin hematoma that precludes brisk walking.
5. Incarcerated.
6. Unable to use mHealth software in English or Spanish.
7. Severe osteoarthritis, or joint replacement within last 3 months.

Parkinson's disease or other progressive movement disorder.

8. Regular use of walker for ambulation.
9. Projected life expectancy <3 months.
10. Clinical judgment concerning other safety or nonadherence issues.
11. Participants admitted from long-term care facility.
12. Currently listed for heart transplant.
13. Left ventricular assist device recipient.
14. Completion of ambulatory cardiac rehabilitation program within prior 3 months.

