10.2 Statistical Hypotheses

Primary Endpoints

Efficacy: 6 minute walk distance (6MWD)

Hypothesis: Degree of improvement in 6MWD will be greater in participants assigned to mHealth-CR than in those assigned to usual care.

Engagement: Mobile health (mHealth) use

CONFIDENTIAL

This material is the property of the NYU School of Medicine and Langone Medical Center. Do not disclose or use except as authorized in writing by the study sponsor

Hypotheses: (1) Among participants offered mHealth-CR, there will be distinct trajectories of engagement (e.g., sustained engagement, disengagement, reengagement, deteriorating engagement); and (2) there will be significant differences in participant characteristics among these groups.

Secondary Endpoints

1. Goal attainment (measured by Goal Attainment Scaling)
2. Health status (measured by SF-12 and SAQ)
3. Activities of daily living (ADLs)
4. Hospital readmission
5. Death

Hypotheses: Goal attainment scaling, health status, and ADLs will improve in participants who are offered mHealth-CR compared with usual care. Hospital readmission and death will be lower in participants who are offered mHealth-CR compared with usual care.

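### Section 10.5 claims 82% power for death by 3 months, while section 4.2.2 expects no detectable mortality difference at the same sample size

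*Combined protocol and SAP*

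**What the plan says.** Section 10.5 (Sample Size) gives a table of secondary outcomes, introduced by "The table below shows clinically meaningful effect sizes for secondary efficacy outcomes, and gives the power to detect these effect sizes". The row for "Death by 3 months" shows an effect size of 10%, no standard deviation, and power of 82%. The power figures are for 320 evaluable patients, "using two-sided, 0.05-level tests; we will not implement multiple comparisons correction for these secondary outcomes". The text before the table also says that the sample gives at least 80% power for effect sizes it calls reasonable in the secondary endpoints. Baseline event rates are attributed to the literature, and none is printed for death.

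Section 4.2.2 (Secondary Study Endpoints) takes a different line: "Given our sample size, we do not expect to detect a significant difference in mortality rates". It adds that a descriptive analysis of death may help put the other endpoints in context and that the rates may help to plan later studies.

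Section 10.2 states a directional hypothesis: "Hospital readmission and death will be lower in participants who are offered mHealth-CR compared with usual care". Section 10.4.3 plans Kaplan-Meier estimates, a logrank test and Cox models for death.

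**The concern.** Section 4.2.2 gives the sample size as the reason for not expecting a significant mortality result. Section 10.5 tables 82% power for mortality at that same sample size, for an effect it labels clinically meaningful. Both statements can be true only if the tabled 10-point effect is one the trial does not expect to see. In that case the row does not describe the trial's real ability to detect a mortality difference.

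What is at stake is interpretation. A non-significant logrank test on a small number of deaths could be cited as a negative result with 82% prespecified power.

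**Working it through.** **Inputs from the documents (10.5).**
- Allocation: "We will randomize 400 participants using a 3:1 allocation, resulting in 300 participants in the intervention group and 100 participants in the usual care group".
- Dropout: "we include adjustment for up to 20% dropout in each arm", which leaves 80 usual care and 240 intervention.
- Two-sided 0.05, effect 10%, stated power 82%.
- Control-arm death rate: not stated, so it has to be back-solved.

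**Is 10% absolute or relative?** A 10% relative reduction gives about 4% to 6% power (pooled test) for control rates from 5% to 20%. The 10% must therefore be 10 percentage points. A 10-point fall requires a control rate of at least 10%.

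**Reproducing 82% with the pooled two-proportion test.** Power = Φ[(d − 1.96·SE0)/SE1]. Here SE0 uses the pooled rate and SE1 the two separate rates. At 14% versus 4%:
- pooled rate = (80×0.14 + 240×0.04)/320 = (11.2 + 9.6)/320 = 0.065
- SE0 = √[0.065×0.935×(1/80 + 1/240)] = 0.0318
- SE1 = √[0.14×0.86/80 + 0.04×0.96/240] = 0.0408
- (0.10 − 1.96×0.0318)/0.0408 = 0.922, so power = 82.2%

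Neighbouring pairs give 89.8% (12% versus 2%) and 78.5% (15% versus 5%).

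**Other formulas.** The control rate at which a 10-point fall gives 82% power, with 80 versus 240:

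| Formula | Control rate | Intervention rate | Relative reduction |
|---|---|---|---|
| Unpooled z | 10.6% | 0.6% | 94% |
| Logrank (Schoenfeld) | about 12.5% | 2.5% | 80% |
| Continuity-corrected | 12.7% | 2.7% | 79% |
| Fisher exact | about 13.5% | 3.5% | 74% |
| Arcsine | 13.7% | 3.7% | 73% |
| Pooled z | 14.05% | 4.05% | 71% |
| Exact chi-square | about 14.6% | 4.6% | 68% |

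For the logrank line, expected deaths = 80×0.125 + 240×0.025 = 16, and the hazard ratio = ln(0.975)/ln(0.875) = 0.190. Then |ln HR|×√(16×0.25×0.75) = 1.663×1.732 = 2.880, and Φ(2.880 − 1.96) = 82.1%. At 14% versus 4% the same formula gives 73%, so the planned test needs a different pair of rates from the pooled test.

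**Against the trial's own population.** Sections 2.3.1 and 5.4 describe clinically stable participants. Section 5.1 requires the ability to do the walk test. Section 5.2 excludes non-ambulatory patients, regular walker users, those admitted from long-term care, and "Projected life expectancy <3 months". Sections 2.3.1 and 7.1.1 keep those with severe cardiac symptoms on the baseline walk out of randomization. A usual-care death rate above 10% in 3 months is hard to reconcile with these criteria, although no document gives the rate.

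**Illustration under assumed rates.** The documents contain neither these control rates nor the halving. Power by exact enumeration of the pooled z-test:

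| Usual care to intervention | 80 versus 240 | 100 versus 300 |
|---|---|---|
| 2% to 1% | 12.9% | 15.2% |
| 3% to 1.5% | 17.2% | 20.0% |
| 5% to 2.5% | 23.8% | 27.2% |
| 8% to 4% | 32.9% | 35.4% |
| 10% to 5% | 38.3% | 42.2% |

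The normal approximation gives 44% for the last entry in the right-hand column.

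**The case against.** The strongest reply is that 82% is not a miscalculation. It can be reached with the plan's own sample at a control rate taken from literature that is cited but not quoted. Power at a stated effect and an expectation that the true effect will be smaller are not logically opposed. This stands. A reader might infer an arithmetic error, or a power that the design cannot have at any rate, and the documents support neither.

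A reader might also take 4.2.2 to say that the sample cannot show a mortality difference. Its wording is softer: it states an expectation and says that a descriptive analysis may be useful. The tension arises because 10.5 calls the tabled effect clinically meaningful and describes the detectable secondary effects as reasonable.

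The back-solved rates are not unique. The table gives no direction, and an increase from 2.3% to 12.3% also gives 82% with the pooled test. That is opposite to the hypothesis in 10.2, so it does not rescue the row.

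The denominator is open to question. Section 4.2.2 ascertains death through the health record at 6 months and 1 year, and 5.7.2 keeps survival data on those lost to follow-up. More than 320 participants may therefore contribute. With 100 versus 300, 82% corresponds to about 16% versus 6%, an even higher control rate.

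Finally, the population has no upper age limit and frailty is measured rather than excluded, so low mortality cannot be taken as given. This is why the illustration runs up to 10%.

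**Conclusion.** Wrong as written, and minor. The stated 82% is undercut by the plan's own text in 4.2.2 and rests on an unstated control rate. With 80 versus 240 and a reduction as hypothesised, every formula tried needs usual-care mortality above 10% (about 10.6% to 14.6%) and a relative reduction of about 70% or more. This does not depend on any assumed rate. The illustrative 13% to 38% does: it rests on assumed control rates of 2% to 10% and an assumed halving.

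A reader might go further and conclude that the logrank test or the directional hypothesis must be withdrawn. The documents do not require that. An underpowered secondary hypothesis is not an error, provided adequate power is not claimed for it. Sample size was set on the 6-minute walk distance, so the primary endpoint is unaffected.

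**What to change.** In 10.5:
- Delete the Death row, or restate it with the assumed usual-care death rate and its source, the test (logrank, to match 10.4.3), the number of participants contributing, and the resulting power. The illustrative figures above should not become protocol text.
- Limit the sentence on at least 80% power for secondary endpoints so that it does not cover death.
- State that death is reported descriptively, consistent with 4.2.2, with a confidence interval for the difference between arms. Section 10.4.1 already plans two-sided intervals.

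Sections 10.2 and 10.4.3 may stay as they are, as long as no adequate power is claimed for death. The cost is a few lines of wording and one less favourable or absent figure. No additional participants are needed, and the conduct and primary analysis of the trial do not change.
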